3.2 Secondary Outcome Measures

3.2.1 Safety

Title: Percentage of participants with occurrence of any serious or targeted adverse event (AE) potentially or definitely related to one-time Levonorgestrel administration.

Description: Adverse events were graded according to the Division of AIDS Table for Grading the Severity of Adult and Pediatric Adverse Events (DAIDS AE Grading Table), corrected Version 2.1, July 2017. Relationship of adverse events to study treatment was determined by the study core team and DAIDS clinical representative.

Time Frame: From study entry to day 28

Analysis Population: Participants who received assigned dose of Levonorgestrel

Reporting Groups: A-D

Associated Study Objective: Secondary Objective #4

Details: Occurrence of the safety outcomes (i.e., number of participants meeting a safety outcome) as defined above will be enumerated and summarized by individual study group. Safety outcomes may be summarized separately by severity grade or type (category or MedDRA grouping) of adverse event. From the protocol definition of the safety outcome, the targeted list of reportable AEs includes the following: grade 3 or higher AEs, grade 2 or higher nausea, diarrhea, menorrhagia or metrorrhagia, and ectopic pregnancies.

Inference: Comparison of the relative number (%) of participants with safety outcome who took single-dose LNG versus the relative number of participants with this outcome who took double-dose LNG, will be performed using the safety analysis comparison set as defined below. The statistical hypothesis test for this comparison will be a Fisher's exact test, using a superiority-testing framework. This comparison may also be repeated for the two following pairwise comparisons:

(1) single-dose LNG versus double-dose LNG among HIV+ women taking EFV-based ART

(2) single-dose LNG among HIV+ women taking DTG-based ART versus double-dose LNG among women living with TB taking RIF-containing TB therapy.

Since this study was not powered to compare occurrence of AEs between LNG double-dose versus single-dose, inference related to comparisons above will focus on describing the magnitude and range of plausible values of observed differences between groups, and will **not** conclude similarity based on the absence of significant differences by Fisher's exact test.

At interim review: Safety (all AE) data will be summarized by cohort and by observed LNG dose group. The only planned formal statistical hypothesis test will be for the safety outcome compared by LNG dose groups (single-dose LNG versus double-dose LNG) using the safety analysis comparison set listed below.

3.2.2 Secondary LNG PK Parameters

Title: LNG PK Parameters calculated based on intensive LNG PK samples obtained from individual participants

Descriptions:

Note: Unless otherwise indicated, standard noncompartmental techniques were used to determine the PK parameter using the software package Phoenix WinNonLin (Certara®).

C_{max}: C_{max} for each participant was the maximum observed concentration.

C_{min}: C_{min} for each participant was the minimum observed concentration after the observed dose among post-dose concentrations. Assay lower limit of quantification for LNG was 0.025 ng/mL; values < LLOQ were imputed as 0.0125.

CL/F: Apparent oral clearance (CL/F) was calculated from the observed LNG concentration from LNG PK samples at pre-dose through 48 hours post-dose. Assay lower limit of quantification for LNG was 0.025 ng/mL; values < LLOQ were imputed as 0 (if pre-dose) or as 0.0125 (if post-dose).

V_d: Volume of distribution (V_d) was calculated for each participant from observed LNG concentration from LNG PK samples at pre-dose through 48 hours post-dose.

T_{1/2}: T_{1/2} for each participant was calculated from the observed LNG concentration from LNG PK samples at pre-dose through 48 hours post-dose. Assay lower limit of quantification for LNG was 0.025 ng/mL; values < LLOQ were imputed as 0 (if pre-dose) or as 0.0125 (if post-dose).

T_{min}: T_{min} for each participant was time to the minimum observed LNG concentration after the observed dose.

Other AUC: AUC for each participant was from LNG concentrations calculated over 24 or 48 hours and modeled to AUC_{infinity} using the linear up/log down version of trapezoidal rule (i.e., noncompartmental technique). This version of the trapezoidal rule uses linear interpolation between untransformed data up to C_{max}, and between log-transformed data from C_{max} through C_{last}. Assay lower limit of quantification for LNG was 0.025 ng/mL; values < LLOQ were imputed as 0 (if pre-dose) or as 0.0125 (if post-dose).

Time Frame: Intensive LNG PK samples within 30 minutes pre-dose, and 0.5, 1, 1.5, 2, 3, 4, 6, and 8, 24 and 48 hours post-dose [adjusting to appropriate time frame above]

Analysis Population: Participants with PK concentrations over 24 or 48 hours and who took both assigned doses of LNG study treatment and expected doses of ART or TB therapy.

Reporting Groups: A-D

Associated study objectives: Primary Objectives 1 and 2, Secondary Objectives 1 and 2

Descriptive Summary Statistics per group:

- **Original scale: n, mean, sd, CV, median, Q1, Q3, min, max**
- **Natural log scaled: geometric mean, 95% CI on GM**

Statistical Analysis Summary: Tables parallel to the Summary table for the primary outcome will be produced for subset of secondary PK parameters, which are based on LNG concentrations. The same reference interval will be used as a comparison for these additional PK parameters. PK parameters not formulated from LNG concentrations (e.g. Tmax, Terminal half-life) will only have descriptive summary statistics.

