#### 5.1.3 Treatment Duration

Study participants will receive one dose of LNG EC on Day 0 and will be followed post-treatment for 4 weeks.

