### 6.2.3 Post-Entry Evaluations

Post-entry evaluations occur after study treatment is administered.

The two final post-dose PK visits should occur 24 hours post-dose  $\pm 2$  hours, and 48 hours post-dose  $\pm 2$  hours. If the visit occurs outside of this window, but within 72 hours of the LNG EC dose, the sample should still be collected.

**The 24 and 48 hours post-dose study visits may only be conducted remotely (e.g., telephone, telehealth) in the following situations during the COVID-19 outbreak:**

- **A participant is unable to attend a visit because of personal illness, COVID illness among others in their home, or local conditions or guidelines restricting travel to the clinic; the site must inform the core team ([[contact]](mailto:[contact])).**
- **The site is temporarily unable to conduct non-essential visits in the clinic; the site must inform the core team ([[contact]](mailto:[contact])).**

**Regardless of the situation, sites should document which visits were conducted remotely, attempt to obtain as much of the visit-specific required information as possible, based on the SOE, and record it on the relevant eCRF. The impacted visits and rationale must be reported and documented, following instructions provided by the team or network leadership.**

Follow-up assessments at 7, 14, and 28 days post entry are conducted by remote contact interview and should occur within the  $\pm 3$  days window.

If clinically indicated (refer to [section 6.3.5](#)), participants will be requested to return to the clinic for a visit.

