#### Premature Study Discontinuation

Women who do not complete the post-dose 8-hour PK study visit to assess LNG concentrations are not evaluable for the primary outcome and will be discontinued from the study and replaced. If the participant does not return for the 24- and 48-hour evaluations or is not reached for the follow-up evaluations on Days 7, 14, and 28, this will be considered a missed visit and the participant will remain on study.

Participants who prematurely discontinue from the study will have the premature discontinuation evaluations performed by remote contact interview or at the clinic prior to being taken off the study, as noted in the Schedule of Evaluations (SOE).

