### 6.3.9 Pharmacokinetic Sampling

Plasma will be obtained for LNG concentrations. Participants will have blood sampling within 30 minutes prior to LNG EC administration, and then 0.5, 1, 1.5, 2, 3, 4, 6, 8, 24, and 48 hours after administration of LNG EC. Participants may leave the clinical site after the 8 hour sample, and return for the 24- and 48-hour samples.

From the same samples collected for LNG analysis, measurement of EFV (Groups A and B), DTG (Group C), and RIF (Group D) concentrations will occur. EFV will be assessed from a sample collected 12-20 hours after the last dose of EFV. DTG or RIF will be assessed from a plasma sample collected 20-28 hours after the last dose of DTG or RIF. To accommodate this timing, EFV should be administered in the evening prior to the entry PK visit and if RIF or DTG are given in the morning, collect pre-dose LNG sample prior to administered DTG or RIF. See the MOPS for further instructions on timing.

The three doses of EFV, DTG, or RIF prior to the entry PK sampling period should be documented on the eCRF. Any EFV, DTG, or RIF dose administered

during the Day 0 PK visit should be documented. On Day 1 and Day 2, document any EFV, DTG, or RIF dose administered since the previous visit.

Additional details regarding LNG, ART, or RIF PK, please see [section 11.3](#), the MOPS, and the laboratory processing chart (LPC) found on the A5375 PSWP.

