### 11.3 Primary and Secondary Data, Modeling, and Data Analysis

#### LNG analysis

The PK parameters for LNG include: maximum concentration ( $C_{max}$ ), time to maximum concentration ( $T_{max}$ ), minimum concentration ( $C_{min}$ ), **time to minimum concentration ( $T_{min}$ )**, oral clearance (CL/F), volume of distribution (Vd), elimination half-life ( $T_{1/2}$ ), and area under the concentration-time curve over 8 hours ( $AUC_{0-8h}$ ), 24 hours ( $AUC_{0-24h}$ ), 48 hours ( $AUC_{0-48h}$ ), and to infinity ( $AUC_{inf}$ ). Standard noncompartmental techniques will be used to determine these PK parameters using the software package Phoenix WinNonLin (Certara®). The AUC (including the primary outcome) will use the linear up/log down version of the trapezoidal rule. This version of the trapezoidal rule uses linear interpolation between untransformed data up to  $C_{max}$ , and between log-transformed data from  $C_{max}$  through  $C_{last}$  [81, 82].  $C_{max}$  will be taken as the maximum observed concentration.  $T_{max}$  is the time at which  $C_{max}$  occurs.  $C_{min}$  will be taken as the minimum observed concentration after the observed dose. Apparent oral clearance will be calculated as  $CL/F = \text{dose}/AUC_{0-24}$  or  $CL/F = \text{dose}/AUC_{0-48}$ . The  $T_{1/2}$  will be determined using regression analysis when possible.

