4.2.2 Primary PK analysis

In addition to the primary PK analyses described above (calculation of GMR and associated 90% CI on LNG PK parameters), the following supplementary analyses will be conducted to test the robustness of results from this primary analysis (based on the primary PK analysis set):

- 1) Parallel analysis of the per-protocol PK set which excludes participants whose measured perpetrator drug concentration was below the pre-defined threshold.
- 2) Estimation of GMR between non-randomized groups, adjusted for prognostic factors, which may be imbalanced between groups. (Note: adjustment will be performed via normal linear regression modeling on log-transformed PK parameters). (Adjusted

GMRs may also be given for the randomized group comparison so that results presented are parallel and this may be interpreted as adjustment for chance imbalance within a small sample size despite randomization.)

Secondary Objective #3: The outcome to address this objective is AUC_{0-24hr}, and the external comparison groups are the LNG groups as published in Pariditpan Contraception, 2017 (Pharmacokinetics of levonorgestrel and ulipristal acetate emergency contraception in women with normal and obese body mass index), and as results available via clinicaltrials.gov NCT:02689804. Within subgroups defined by normal BMI and obese BMI, the GMR and associated 90% CI for AUC_{0-24hrs} for LNG will be estimated between A5375 Group C (DTG) and this external historical control group. (This analysis will use Satterthwaite calculation of standard error.)

Secondary Objective #5: The outcomes to address this objective including the primary outcome (LNG AUC₀₋₈ hours), as well as the following: C_{max}, and AUC₄₈, C₄₈ (or AUC₂₄ and C₂₄, if too many participants are missing PK parameters at 48 hour). The independent variables include the baseline measurements of body weight including body fat percentage, total weight in kg, and BMI in kg/m². To evaluate the association between these baseline independent variables and the outcome of log-transformed LNG PK parameters, generalized linear regression models will be fit, with additional explanatory variable of LNG dose and perpetrator drug. Geographic region and age will be included for in these models to provide calculation of adjusted GMRs where possible.

5 Report Contents

1. *CONSORT Diagram*
 - a. *Screening and screen failures*
 - b. *Enrollment and eligibility violations*

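### LNG Cmin after a single dose has no nominal time, so its between-group GMR would depend partly on when each woman gave her last sample

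*SAP*

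**What the plan says.** Both documents define Cmin the same way. Protocol 11.3 says that it "will be taken as the minimum observed concentration after the observed dose"; SAP 3.2.2 says that Cmin "for each participant was the minimum observed concentration after the observed dose among post-dose concentrations". Neither fixes a time or restricts the search to samples after Tmax. In SAP 3.2.2, values below the 0.025 ng/mL limit are set to 0.0125 for Cmin.

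Dosing and sampling: protocol 5.1.3 says "Study participants will receive one dose of LNG EC on Day 0", and protocol 6.3.9 schedules a pre-dose sample "and then 0.5, 1, 1.5, 2, 3, 4, 6, 8, 24, and 48 hours after administration of LNG EC".

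Several provisions let the time of the last sample vary:
- Protocol 6.2.3 gives the 24 h and 48 h visits a window of ±2 h, then adds: "If the visit occurs outside of this window, but within 72 hours of the LNG EC dose, the sample should still be collected". It also lets these visits be remote in certain COVID-19 situations.
- Protocol 6.2.4, on women who do not return at 24 and 48 h: "this will be considered a missed visit and the participant will remain on study".
- The SAP 3.2.2 analysis population begins "Participants with PK concentrations over 24 or 48 hours".
- SAP 4.2.2 foresees missing late data. For Secondary Objective 5 it replaces the 48 h measures with 24 h ones "if too many participants are missing PK parameters at 48 hour".

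On comparison, protocol 10.6.3 analyses the other LNG PK parameters in parallel with the primary outcome. SAP 3.2.2 plans tables like the primary one, with the same reference interval, for a subset of the concentration-based parameters. Parameters not built from concentrations, with Tmax and half-life as examples, are descriptive only.

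**The concern.** Cmin is meaningful as a trough within a dosing interval. After one dose the concentration keeps falling, so the minimum is mostly a record of how late the woman was last sampled. A woman who returns at 48 h contributes a 48 h value. One who comes only at 24 h contributes a value that is higher for no pharmacological reason. In a slow absorber, the 0.5 h sample can be the lowest instead.

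The comparisons B vs C, D vs C and A vs C are not randomised. These groups differ by regimen, B/C/D also by disease, and possibly by country, so equal return rates at 24 and 48 h cannot be assumed. A Cmin GMR set against (0.7, 1.43) would then mix the drug effect with attendance. It could be read alongside the primary result, because SAP 3.2.2 links these secondary parameters to Primary Objectives 1 and 2.

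**Working it through.** **The plan's own figure.** The documents give no figure for Cmin. The design figure behind the reused interval is 88% power for AUC0-8h (SAP 2.3: 30 per group, CV 0.45, true GMR 100%, bounds 70-143%). It reproduces:
- Log-scale SD = sqrt(ln(0.45² + 1)) = 0.429, and SE = 0.429 × sqrt(2/30) = 0.111.
- Two one-sided 5% tests with 58 df give 87.7% power by simulation.
- The typical 90% CI is exp(±1.67 × 0.111) = 0.83 to 1.20, as stated.

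**Inputs for Cmin.** Half-lives come from protocol 2.1.1: 27.5 h in 30 healthy volunteers, 44 h for another formulation, and 17 to 24 h as a general range. Decline is taken as mono-exponential after 8 h (assumption).

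**Effect of the last sampling time.** The ratio of a value at time t to the 48 h value is 2^((48 − t)/half-life):

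| Half-life | Last sample 24 h | Last sample 72 h |
|---|---|---|
| 17 h | 2.66 | 0.38 |
| 24 h | 2.00 | 0.50 |
| 27.5 h | 1.83 | 0.55 |
| 44 h | 1.46 | 0.69 |

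**Effect on the GMR with no PK difference.** If a fraction p more of one group ends at 24 h instead of 48 h, the GMR is multiplied by (24 h/48 h ratio)^p. The documents give no attendance figures, so p is assumed over a range:

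| p | 17 h | 27.5 h | 44 h |
|---|---|---|---|
| 0.05 | 1.05 | 1.03 | 1.02 |
| 0.10 | 1.10 | 1.06 | 1.04 |
| 0.20 | 1.22 | 1.13 | 1.08 |

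Attendance alone would reach 1.43 only at p = ln(1.43)/ln(ratio), which is 0.37, 0.59 and 0.95 at 17, 27.5 and 44 h. For scale, protocol Table 10.4-2 (AUC, CV 0.45, same bounds) has power falling from 88% to 84% and 72% as the true GMR moves from 100% to 95% and 90%. The CV of Cmin is not given, so no power figure for Cmin can be computed.

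**Early minimum.** In a one-compartment model with a 27.5 h half-life (k = 0.0252/h), the 0.5 h value is 0.70 of the 48 h value at an absorption rate of 0.5/h. It is 0.72 at 1/h with a 0.25 h lag, and 1.28 at 1/h without lag (all rates assumed). The first two cases imply Tmax = lag + ln(ka/k)/(ka − k) = 6.3 h and 4.0 h. The protocol's Tmax range is 1 to 4 h, so this route concerns slow absorbers at or beyond its edge.

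If such a 0.5 h value were also below the assay limit, the group geometric mean would be multiplied by exp(−(m/30) × ln(c/0.0125)), where m is the number of such women and c the late value that should have counted. Taking c from 0.5 (assumed) to 2.3 ng/mL (307.5 × 0.0252 × exp(−48 × 0.0252), from the protocol's AUCinf), one woman in 30 lowers it by 12-16%. The documents do not say how often this would occur.

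**After the fix.** At a fixed 48 h, the ±2 h window leaves factors of 1.05 and 0.95 at a 27.5 h half-life, and a 0.5 h value can no longer be selected.

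**The case against.** The strongest reply is that this matters little. Cmin is one of several secondary PK parameters, and no decision rule rests on it. Protocol 2.1.1 says that no PK parameter has been tied to LNG EC effectiveness. Late exposure is also covered by AUC0-24h, AUC0-48h, AUCinf, CL/F and half-life. Secondary Objective 5 already models log C48 (or C24) with LNG dose and perpetrator drug as explanatory variables. B vs A is randomised, which reduces the attendance concern there. All of this stands and limits the importance of the point. It does not repair the definition: the Secondary Objective 5 models are aimed at body size, and the SAP does not set their group contrasts against the No-Effect Bounds.

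A second reply is that the comparison is inferred. SAP 3.2.2 does not name Cmin in its subset, and table outlines are left to an Analysis Implementation Plan that is not available here. That is correct. Inclusion is likely, because Cmin is a concentration and protocol 10.6.3 covers the other PK parameters without restriction, but it is not certain.

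Third, the sizes depend on assumed attendance differences. They do, so a range is given. None of the shifts shown alone reaches 1.43.

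A reader might also go further than the documents allow in three ways:
- **8 h values as Cmin.** Protocol 6.2.4 keeps women with only 8 h data on study, but the SAP 3.2.2 population, read literally, excludes them from these parameters.
- **72 h values as a settled part of Cmin.** Protocol 6.2.3 says that late samples are collected, not that they enter Cmin, and the SAP time frame ends at nominal 48 h.
- **Tmin compared between groups.** Tmin is a time, like Tmax, so it naturally falls under descriptive reporting. It shows when each minimum occurred, though it does not correct Cmin.

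**Conclusion.** The point holds for a secondary outcome. Cmin as defined has no nominal time, and its value depends on whether the last sample was at about 24 or 48 h (possibly up to 72 h), or on slow absorption. The firm part is the 1.5- to 2.7-fold difference between a 24 h and a 48 h value, which follows from the protocol's half-lives under mono-exponential decline. The resulting GMR shift, about 2-5%, 4-10% or 8-22% for 5, 10 or 20 percentage points of differential attendance, is conditional on an imbalance that the documents neither state nor rule out. That Cmin will be set against (0.7, 1.43) is the likely reading, not an explicit statement. Doubt about the primary conclusions would not follow: AUC0-8h uses samples to 8 h only and is untouched.

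**What to change.** In protocol 11.3 and SAP 3.2.2, replace Cmin in any between-group GMR by C24h and C48h. Take each from a sample within its ±2 h window, or interpolate log-linearly to the nominal time between samples that bracket it, and set it to missing otherwise. List by name the parameters that get GMR tables, so that the status of Cmin is not left to inference.

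If Cmin must stay for the registry record, report it descriptively beside Tmin and restrict it to samples after Tmax. Tmin needs no change.

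The cost is wording in the protocol and SAP and the matching registry outcome text; no new samples are needed. The downside is that women without a 48 h sample drop out of C48h, so that analysis is itself selected on attendance. Reporting C24h beside it, with the number of women contributing per group, makes this visible.

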#### 2.1.1 Levonorgestrel (LNG)

Levonorgestrel is a progestational agent that inhibits ovulation by interrupting follicular development, and inhibits fertilization by altering the tubal transport of sperm and/or ova. In addition, it may inhibit implantation by altering the endometrium, but it is not effective once the process of implantation has begun [21]. LNG is commonly used in combination oral contraceptive pills, as EC, in progestin-releasing subdermal implants, and intrauterine devices. As EC, LNG should be taken within 72 hours after unprotected intercourse to prevent pregnancy. The absolute effectiveness of EC is difficult to determine because the rate varies with the timing of dosage with respect to unprotected intercourse, ovulation, and with the type of EC used. Estimates of LNG efficacy range from 59-94% [22]. In a multicenter randomized comparison of LNG versus ulipristal in nearly 1700 women presenting to family planning clinics for EC, there were 37 pregnancies with no statistical difference observed between the groups. To increase the power of the study, a meta-analysis was performed, and data from a total of 2221 women randomized to either ulipristal or LNG were compiled. This analysis confirmed that the pregnancy rate in both groups was lower than predicted, and that the pregnancy rate for LNG was 2.6% [23].

LNG for EC is typically given as a single 1.5 mg dose within 72 hours after intercourse. LNG reaches maximum concentration approximately 1.7 (range 1-4)

hours after administration and is 100% bioavailable after oral administration [21, 24, 25]. In 30 healthy, female volunteers, the mean (SD) LNG  $C_{max}$  was 19.1 (9.7) ng/mL, area under the curve  $(AUC)_{inf}$  was 307.5 (218.5) ng\*hr/mL, and half-life was 27.5 hours [21]. A clinical evaluation of another formulation of LNG (0.75 mg tablets, two tablets once) in five healthy volunteers found a geometric mean 44-hour (39-48-hours) half-life [26].

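### AUCinf may be extrapolated from profiles that end at 24 h; if induction shortens the half-life, this understates AUCinf more in control Group C and pushes the B/C and D/C ratios upward

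*SAP*

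**What the plan says.** SAP 3.2.2 covers AUC0-24h, AUC0-48h and AUCinf in one entry: "AUC for each participant was from LNG concentrations calculated over 24 or 48 hours and modeled to" infinity. The analysis population for the secondary PK parameters is "Participants with PK concentrations over 24 or 48 hours and who took both assigned doses of LNG study treatment", plus the expected ART or TB doses. In the same section T1/2 "was calculated from the observed LNG concentration from LNG PK samples at pre-dose through 48 hours post-dose", and CL/F and Vd use the same window.

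Protocol 6.3.9 schedules samples before dosing "and then 0.5, 1, 1.5, 2, 3, 4, 6, 8, 24, and 48 hours after administration of LNG EC", so only two samples follow the 8 h draw.

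Three passages make profiles without a 48 h sample foreseeable:
- Protocol 6.2.4 (Premature Study Discontinuation): "If the participant does not return for the 24- and 48-hour evaluations", this counts as a missed visit and the woman stays on study.
- Protocol 6.2.3: "The 24 and 48 hours post-dose study visits may only be conducted remotely" in listed COVID-19 situations. A remote visit yields no blood.
- SAP 4.2.2, Secondary Objective #5, has a fallback to 24 h parameters if too many 48 h parameters are missing.

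Protocol 11.3 estimates T1/2 by regression when that is possible. Neither document states the last sample needed for AUCinf, terminal-slope criteria or a limit on extrapolation. SAP 3.2.2 compares an unnamed subset of the concentration-based secondary parameters with the primary No-Effect Bounds.

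Half-life is given as 27.5 h and as "geometric mean 44-hour (39-48-hours) half-life" in Protocol 2.1.1, which later also gives 17–24 h.

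**The concern.** A profile that ends at 24 h takes its terminal slope from about 6, 8 and 24 h, when distribution is still contributing to the decline. The slope is then too steep and the extrapolated tail too small. The loss is greater where the half-life is longer. If EFV or RIF shortens the LNG half-life, the longer half-life belongs to control Group C, so the denominator of B/C and D/C is understated more than the numerator.

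AUCinf is the listed parameter closest to total exposure and a natural check on an 8 h primary outcome. An upward shift in its GMR could make an incomplete correction of the interaction look more complete than it is.

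**Working it through.** **1. The plan's own figure.** The documents give no bias figure for AUCinf, so the similarity rule itself was reproduced. SD = sqrt(ln(0.45² + 1)) = 0.429, with n = 30 per group and 58 df. Power for a 90% CI inside (0.70, 1.43) at true GMR 1.00 is 87.6% (stated 88%). The typical CI is 0.831–1.204 (stated 83–120%).

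**2. Is the decline multiphasic?** Protocol 2.1.1 gives Cmax 19.1 ng/mL and AUCinf 307.5 ng·h/mL. One-phase decay from Cmax has area Cmax × half-life / ln 2:
- 17 h: 19.1 × 17 / 0.693 = 468
- 24 h: 661
- 27.5 h: 758

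All far exceed 307.5, so one-phase decline does not fit the protocol's figures.

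**3. Model.** Two-compartment oral model matched to Cmax 19.1, AUCinf 307.5, Tmax 1.7 h and each quoted half-life.
- Assumed: distribution half-life 2–5 h; induction as higher clearance; terminal slope by best adjusted R² on at least three points.
- The EFV effect is the 57% AUC reduction in Protocol 2.2, so the true double-dose GMR is 2 × 0.43 = 0.86.
- Linear-up/log-down AUC is computed at the protocol's times, and AUCinf = AUC0-last + Clast/slope.

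With 24 h profiles the apparent control half-life is about 9–13 h when the truth is 17–27.5 h.

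**4. Results.** Recovery is estimated over true AUCinf in Group C. The factor is estimated over true GMR, and the last figure is 0.86 × factor.

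| Control half-life | Last sample | Group C recovery | Factor | GMR read (true 0.86) |
|---|---|---|---|---|
| 17 h | 24 h | 0.91–0.93 | 1.07–1.09 | 0.92–0.93 |
| 24 h | 24 h | 0.82–0.85 | 1.13–1.16 | 0.97–1.00 |
| 27.5 h | 24 h | 0.79–0.82 | 1.15–1.20 | 0.99–1.03 |
| 44 h | 24 h | 0.65–0.74 | 1.21–1.31 | 1.04–1.13 |
| 17 h | 48 h | 0.99–1.00 | 1.01–1.03 | 0.87–0.89 |
| 24 h | 48 h | 0.95–0.98 | 1.04–1.08 | 0.89–0.93 |
| 27.5 h | 48 h | 0.92–0.97 | 1.05–1.10 | 0.91–0.94 |
| 44 h | 48 h | 0.81–0.85 | 1.14–1.18 | 0.98–1.02 |

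Example (24 h half-life, 3 h distribution, all profiles ending at 24 h): Group C 0.824 × 307.5 = 253. Induced double dose: true 0.86 × 307.5 = 264.5, recovery 0.824 × 1.164 = 0.959, estimate 254. The ratio is 0.86 × 1.164 = 1.00.

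**5. When only some profiles end at 24 h.** With share p in both groups, the factor is F48^(1−p) × F24^p, so the 24 h profiles add (F24/F48)^p. For half-life 17–27.5 h, F24/F48 runs from 1.076/1.034 = 1.041 to 1.186/1.053 = 1.126.

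| p | Total factor | Added by 24 h profiles |
|---|---|---|
| 10% | 1.02–1.10 | 0.4–1.2% |
| 25% | 1.03–1.12 | 1–3% |
| 50% | 1.04–1.14 | 2–6% |

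**6. Effect on a similarity call, if the bounds are applied (n = 30).** At true GMR 0.70 and CV 0.45, the chance of declaring similarity rises from 5% to 11% (factor 1.05), 17% (1.08) or 46% (1.19). At CV 0.71, which is the protocol's AUCinf spread (218.5/307.5), it rises from 5% to 8%, 10% or 22%. At true GMR 1.00 and CV 0.45, a factor of 1.15 lowers it from 88% to 61%.

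**7. Cases with no bias.** If induction acts only through first-pass loss, the factor is 1.00. If decline is one-phase, recovery is 0.999–1.001.

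**The case against.** The more natural reading of the SAP entry is that 24 or 48 hours names AUC0-24h and AUC0-48h, with AUCinf appended. T1/2 is defined on samples through 48 h, and it comes from the same slope that AUCinf needs. Further detail is deferred to the Analysis Implementation Plan, which was not available. This has force: a 24 h AUCinf is permitted by the text, not prescribed. But nothing in either document keeps a woman without a 48 h sample out of AUCinf.

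The 48 h sample is scheduled for everyone, remote visits are confined to listed situations, and samples outside the window are still taken up to 72 h. No missing rate is given. This stands, and it makes the all-at-24 h rows an upper limit.

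AUC0-8h is the primary outcome, AUC0-24h and AUC0-48h are also reported, and Secondary Objectives 3 and 5 do not use AUCinf. This also stands.

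A reader might go further in four ways that the documents do not support:
- **That the error always favours similarity.** It is upward. At a true GMR of 1 or more it moves away from similarity, and Protocol 2.1.2 (a reduction of 50% or more with RIF) allows a GMR of 1.00.
- **That the shortfall equals the one-phase tail beyond 24 h.** One-phase decay conflicts with the protocol's Cmax and AUCinf, and would produce no shortfall.
- **That a GMR near 1 is the expected reading when the truth is 0.86.** That requires every profile to end at 24 h.
- **That AUCinf is expressly held to (0.70, 1.43).** It qualifies for the subset but is not named.

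**Conclusion.** A minor but real gap in a secondary analysis. The SAP permits AUCinf from 24 h profiles. At control half-life 17–27.5 h, such profiles understate AUCinf by about 7–21% in Group C and 0–6% in an induced double-dose group. The GMR is inflated by about 7–20% if all profiles end at 24 h. At missing rates of 10–25% in both groups, the 24 h profiles add about 0.4–3%. About 1–10% remains with complete 48 h sampling, and more if the 44 h half-life applies.

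This rests on three assumptions: a distribution half-life of 2–5 h, a default slope rule, and induction that shortens the half-life. The documents attribute the interaction to CYP3A induction but do not separate first-pass from systemic effects. The shift is towards similarity where the true GMR is below 1, as the EFV figure of 0.86 suggests. The primary AUC0-8h result is unaffected.

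**What to change.** In SAP 3.2.2:
- Derive AUCinf and its terminal slope only in women with a 48 h sample (the visit window opens at 46 h) or a later one.
- Report by group the extrapolated percentage and the number of women excluded for lack of that sample.
- State whether AUCinf is in the subset compared with (0.70, 1.43).
- Note that some upward bias, about 1–10% under the assumptions above, remains even with 48 h samples.

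A cap on the extrapolated share would not do the same job. The steep slope shrinks the apparent share too: with 24 h profiles it reads only about 16–26% in the model.

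The cost is a few sentences of SAP text and a slightly smaller AUCinf set. No new samples are needed.
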